Co-investigators	
[name] University of Warwick [contact]
 
Associate [name] University of Warwick/University of Birmingham [contact]/[contact]
 
[name] University of Warwick/University of Birmingham [contact]/[contact]
 
[name] University of Warwick [contact]
 
[name] University of Warwick [contact]
 
[name] University of Warwick [contact]
 
[name] Kings College Hospital NHS Foundation Trust [contact]
 
[name] Hull University Teaching Hospitals NHS Trust [contact]
 
[name] County Durham and Darlington NHS Foundation Trust [contact]
 
[name] University of Warwick

	
[contact]
 
[name] University of Warwick/University of Birmingham [contact]/[contact]
 
[name] PPI Representative
 
[name] PPI Representative
 
[name] PPI Representative

Sponsor	
[name] Research and Development Department UHCW NHS Trust [name] [contact] [contact]

Funder	
National Institute for Health Research (NIHR) [name] [contact]

Trial Co-ordination Centre	
[name] Trial Manager UHCW NHS Trust [name] [contact] [contact]

STUDY SUMMARY

Full study title	SUMU-Endo: Single-use versus Multiple-use Endoscopes in Gastroenterology: Multi methods analysis to balancing infection control and environmental impact
Short study title	SUMU-Endo
Study aim	To explore the views and experiences of patients receiving endoscopy and staff involved in procuring, using, cleaning and decontaminating endoscopes.
Study design	A multi-centre mixed-methods qualitative study using interviews and focus groups.
Study participants	Patients who have had an endoscopy in the NHS. NHS staff involved in supply chain, decontamination of endoscopes.
Planned Size of Sample	30 NHS Patients 30 NHS Staff
Planned Study period	18 months
Planned recruitment start date	01 Aug 2024
Planned recruitment end date	30 September 2025
Planned study end date	31 December 2025
Objectives	
Patient interviews
 
1. To explore the views and experiences of patients receiving endoscopy in the NHS
 
Staff focus groups/interviews
 
1. To explore the views and experiences of staff involved in procuring, using, cleaning and decontaminating endoscopes in the NHS.

STUDY FLOW CHART

[figure not shown]

Figure 1: Flow of participants through the study

SCHEDULE OF EVENTS

Table 1: Schedule of Events

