1.3 Proposed study

This project is taking place as part of Work Package 4 (WP4, see Figure 1). A range of data collection methods will be used to discern the attitudes and experiences of NHS patients receiving endoscopy, and staff working in the NHS who handle colonoscopes and other GI endoscopes before and after use (e.g., selection, procurement, disinfection, and disposal of endoscopes).

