1.4 Study population

Patients who have had or are awaiting an endoscope in the NHS will be approached for this study, as well as staff working in the NHS involved in the life cycle of endoscopes.

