2 OBJECTIVES

2.1 Primary objective

To explore the views and experiences of patients receiving endoscopy and staff involved in procuring, performing endoscopies, cleaning and decontaminating endoscopes.

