5. ELIGIBILITY CRITERIA

5.1 Inclusion criteria

Patients

- Over the age of 18
- Patient has been invited to an NHS endoscopic clinic to undertake an upper GI endoscope procedure, including diagnostic endoscopies and the less complex therapeutic endoscopy.
- Patient is able to read and understand information provided
- Patient has capacity to provide consent
- Patient is able to participate in an interview.

Staff

- Over the age of 18
- Employed by the NHS
- Working in relevant endoscopy unit - primary work involves the conduct of endoscopy and/or waste disposal services (decontamination or disposal).

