6. STUDY PROCEDURES

6.1 Sampling

6.1.1 Size of sample

No sample size calculation was derived as this is a qualitative study where we aim to maximally sample participants across the units (not depth of investigation at each unit). We will use maximum variation sampling based on the following parameters: age, ethnicity, gender for all participants, and years of experience for NHS staff.

Patients

We plan to interview 5 patients from 6 sites but recognise that flexibility needs to be maintained to ensure diversity in the participant sample.

Staff

The planned number of staff participants is 30 (5 staff from 6 sites) but we will allow flexibility within units, for example if one participant performs both selection and procurement.

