6.2 Recruitment

Patients

We will conduct interviews with patients from 6 hospitals. The PI and research team at each site will identify potential participants through the clinic list. Potential participants who require an endoscopy will be asked if they are interested in the study and given study documentation in person. Alternatively, patients can be sent an invitation letter, PIS and consent form via post and be given at least 24 hours to decide if they would like to take part.

Interested patients can contact the research team using the details provided in the study documents. Alternatively, they will be contacted after a reasonable amount of time has passed with no response to see if they are interested. If they agree to take part, consent will be obtained either in-person at attendance of the clinic, or via the telephone if necessary.

Staff

The PI and research team at each site will generate a list of all staff who work across the endoscopy pathway and identify potential study participants. Participants will be invited to take part in the study via email invitation along with the PIS from the site PI, or informed about the study in person and given a PIS.

Staff will have at least 24 hours to decide if they'd like to take part. If they agree, the PI and research team at site will then contact the member of staff to consent them in-person. Their contact details will be provided to the experienced qualitative researcher after consent who will then organise a focus group consisting of 2-5 members of staff on Microsoft Teams. However if this is not possible, an individual interview will be scheduled. Staff recruitment will continue until all segments of the extended endoscopy care pathway are accounted for, or when saturation is reached in the data collection.

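### The staff inclusion criterion, read literally, shuts out NHS staff whose main job is selecting, procuring or supplying endoscopes, although the objective and study summary count them in

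*Protocol*

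**What the plan says.** The staff criterion in Protocol Section 5.1 sets a workplace and a type of primary work: "Working in relevant endoscopy unit - primary work involves the conduct of endoscopy and/or waste disposal services (decontamination or disposal". The only other staff conditions are age and NHS employment. The exclusion in Section 5.2 that bears on staff removes only non-NHS providers.

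Elsewhere the protocol describes the staff group more widely:

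- Study Summary, participants: "NHS staff involved in supply chain, decontamination of endoscopes".
- Study Summary, staff objective: "To explore the views and experiences of staff involved in procuring, using, cleaning and decontaminating endoscopes in the NHS".
- Section 1.3, staff who handle endoscopes before and after use: "e.g., selection, procurement, disinfection, and disposal of endoscopes".
- Section 1.4: "staff working in the NHS involved in the life cycle of endoscopes".
- Section 2.1, primary objective: "staff involved in procuring, performing endoscopies, cleaning and decontaminating endoscopes".
- Section 6.1.1, on flexibility in staff numbers: "for example if one participant performs both selection and procurement".

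Section 6.2 has sites list staff across the endoscopy pathway and recruit "until all segments of the extended endoscopy care pathway are accounted for", or until saturation, whichever applies.

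**The concern.** Eligibility is the operative text. Table 1 places the eligibility assessment at screening, and Section 6.4 trains site staff to confirm it. If Section 5.1 is narrower than the objective, the criterion decides who is interviewed.

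The project is meant to inform NHS decision makers on single-use versus multiple-use endoscopes. Section 1.2 says this study will feed a logic model of the endoscope's extended life cycle, reaching beyond clinical care. Staff who select, buy and supply endoscopes belong to that life cycle. If those who do this as their main job are screened out, their accounts are missing from the data and no later analysis can supply them.

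**Working it through.** No power or precision calculation applies to this qualitative study. The one figure involved is the staff sample: 5 staff × 6 sites = 30, which agrees with the Study Summary. It is not in dispute.

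The check is a comparison of the staff functions named in each place with the primary work that Section 5.1 admits: carrying out endoscopy, decontamination, or disposal. Cleaning and disinfection are counted here as decontamination.

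| Place | Staff functions named | Not admitted as primary work |
|---|---|---|
| Section 2.1 | procuring, performing, cleaning, decontaminating | procuring (1 of 4) |
| Study Summary, staff objective | procuring, using, cleaning, decontaminating | procuring (1 of 4) |
| Study Summary, participants | supply chain, decontamination | supply chain (1 of 2) |
| Section 1.3 (examples only) | selection, procurement, disinfection, disposal | selection, procurement (2 of 4) |
| Section 6.1.1 (example) | selection and procurement | both, if they are the person's main work |
| Section 1.4 | endoscope life cycle, no list | not countable |
| Section 1.1, Work Package 4 | using, cleaning, decontaminating | none |

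The next question is whether any other text repairs the mismatch.

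1. **Section 4** draws participants from people who work in, or use, the sites' endoscopy services. It does not name procurement and does not override Section 5.1.
2. **Section 6.2** starts from a broad list of pathway staff, but those listed must still meet Section 5.1.
3. **Section 6.1.1** varies the sample by age, ethnicity, gender and years of experience. Role is not a sampling parameter, so nothing reserves a place for procurement.
4. **The stopping rule in Section 6.2** joins two conditions with an *or*. Saturation among the roles that are admitted is enough to stop, even if no dedicated procurement or supply-chain employee has taken part.
5. **Section 10.1** gives a change to eligibility criteria as an example of a substantial amendment, so sites should not widen the criterion informally.

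None of these admits the missing roles.

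**The case against.** The strongest reply is that Section 5.1 restricts the workplace and the primary work but does not bar other duties. An employee of the unit who mainly carries out endoscopy or decontamination, and also chooses or orders endoscopes, is eligible. The example in Section 6.1.1 appears under flexibility within units, which suggests the authors pictured procurement as a task that unit staff share. This stands. A reader might infer that the procurement part of the objective cannot be answered at all, and the documents do not support that.

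A reader might also infer that the rule to cover every pathway segment traps recruitment in a condition it cannot meet. It does not, because saturation is a stated alternative. That alternative does, however, let the gap pass unnoticed.

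The Work Package 4 description in Section 1.1 leaves procuring out, so Section 5.1 is not the only narrow statement. This also stands. It shows that the scope is inconsistent in more than one place, and it means that narrowing the objective is a legitimate way to resolve the conflict.

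Two further inferences should not be drawn. The protocol does not say where procurement or decontamination staff are based, so it cannot be claimed that decontamination staff in a separate department are excluded in practice. Nor does it say who decides whether single-use endoscopes are bought.

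What the reply does not remove is the mismatch for dedicated staff. Someone whose primary work is procurement or supply fails Section 5.1 wherever they sit.

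**Conclusion.** The criterion is wrong as written, in a limited sense. Section 5.1 contradicts the Study Summary and Sections 1.3, 1.4, 2.1 and 6.1.1 for staff whose primary work is selecting, procuring or supplying endoscopes. As it stands, one of the four staff functions in the primary objective would be informed only by people for whom it is a secondary duty, and recruitment could finish without any dedicated procurement or supply-chain participant.

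It would go too far to say that the objective and sample are defined around procurement. Procuring is one of several functions in the objective. The summary's participant line gives supply chain more prominence, but that line is itself incomplete because it omits staff who perform endoscopy.

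The conclusion assumes that sites apply Section 5.1 literally. The number of staff lost cannot be estimated, since the protocol gives neither a quota nor a count by role.

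**What to change.** Reword the staff criterion to admit NHS employees whose role includes selecting, procuring or supplying, using, cleaning or decontaminating, or disposing of GI endoscopes for a participating site, whether or not they are based in the endoscopy unit. Then align three other places:

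- the participant line in the Study Summary, adding staff who perform endoscopy;
- the Work Package 4 description in Section 1.1, adding procuring;
- the sampling sentence in Section 4, so that it does not confine staff to those working in endoscopy services.

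If the sponsor does not intend to recruit procurement and supply-chain staff, take procuring and supply chain out of the objective and summary instead, and bring Sections 1.3, 1.4 and 6.1.1 into line.

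The cost of the first option is an eligibility amendment, communicated as Section 10.1 requires for substantial changes, and contact between sites and their procurement staff. No extra participants are needed: the plan stays at 30 staff. The change should be made while recruitment is open, because staff who were screened out cannot be added at analysis.

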5.2 Exclusion criteria

- Patient has received a lower GI endoscopy, e.g. colonoscopy or sigmoidoscopy
- Non-NHS service providers and receivers. (e.g., private diagnostic clinics)

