2.2 Primary outcome measures

As this is a qualitative study, there is no primary outcome measure. However, the aim is to present the experience, attitudes and values of staff and patients in narrative form (final report and publication) and in visual summary formats (infographics), to be shared across the relevant networks and contribute to the overall study aim of providing evidence for NHS decision makers on the use of single-use vs. multiple-use endoscopes in gastroenterology.

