4. STUDY SETTING

This study will be multi-centre, across 6 sites in England, Scotland and Wales. The only requirement for entry into the study is that the hospital site deliver endoscopy services.

Using professional networks and links with The British Society of Gastroenterology, gastroenterology units have been identified to participate in the study. Participants (staff and patients) will be sampled from those people who work in or access endoscopy services at these sites.

Some sites will be large tertiary centres which do complex endoscopic procedures, others will be District General Hospitals who do the vast majority of diagnostic endoscopies and the less complex therapeutic endoscopy. It is essential that ED&I is attended to in the selection of sites and participants to ensure a representative sample is obtained, and conclusions and recommendations can be drawn that are appropriate to the population in the UK. The aim will be for maximal variation in the sample, both in terms of the hospitals recruited (local population and geography) and the NHS staff and patients who are invited to participate (e.g., age, gender, ethnicity). The local population of the centres will include rural and urban areas with residents of mixed socioeconomic status.

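### The patient eligibility criteria admit upper GI endoscopy only, while the stated population, objective and use of the findings cover GI endoscopy in general, and the lower GI exclusion has no time frame.

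*Protocol*

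**What the plan says.** **Eligibility.** Among the patient inclusion criteria, Section 5.1 requires: "Patient has been invited to an NHS endoscopic clinic to undertake an upper GI endoscope procedure". Section 5.2 then excludes on this ground: "Patient has received a lower GI endoscopy, e.g. colonoscopy or sigmoidoscopy". It gives no period and does not say whether the clause means the procedure that brought the patient to the clinic or any earlier one.

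**Population and objective.** The Study Summary lists the patient participants as "Patients who have had an endoscopy in the NHS". Section 1.4 says: "Patients who have had or are awaiting an endoscope in the NHS will be approached for this study". The primary objective in Section 2.1 begins: "To explore the views and experiences of patients receiving endoscopy and staff involved in procuring". Section 6.2 has sites approach people on the clinic list who need an endoscopy. None of these is limited to upper GI.

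**Use of the findings.** Section 1.2 sets the scope limit at endoscopes used in gastroenterology. Section 2.2 says that the work feeds the overall aim of "providing evidence for NHS decision makers on the use of single-use vs. multiple-use endoscopes in gastroenterology".

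**Staff.** Section 1.3 describes the staff group as "staff working in the NHS who handle colonoscopes and other GI endoscopes before and after use". The staff criteria in Section 5.1 carry no upper GI limit.

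**Sampling and analysis.** Section 4 aims for maximal variation and a representative sample. Section 6.1.1 names age, ethnicity and gender as the variation parameters for patients. Section 3.2 analyses patient and staff data separately and sets them against each other only where that is appropriate.

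**The concern.** In a purposive sample of this size, the eligibility criteria largely fix what can be concluded, and analysis cannot supply the views of people who were never allowed to enter. There are two problems here.

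First, the question is put for patients having endoscopy, but the criteria answer it for upper GI patients only. A reader of the report who relied on the objective would take the patient findings to cover colonoscopy and sigmoidoscopy. Where staff and patient views are compared, a difference could reflect the type of scope or procedure rather than the viewpoint, because the staff group extends to colonoscopes.

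Second, the open-ended exclusion can be applied in two ways. Six sites screening from their own clinic lists may apply it differently, so the make-up of the patient sample would depend on local interpretation.

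**Working it through.** The study is qualitative and has no power calculation, so the check is mainly a comparison of texts. *Index procedure* below means the endoscopy for which the patient was identified.

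**1. The plan's own figure.** Section 6.1.1 gives 5 patients from each of 6 sites: 5 × 6 = 30. This agrees with the 30 NHS patients in the Study Summary. The number is not in dispute.

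**2. Who can enter.** Apply Sections 5.1 and 5.2 to three kinds of patient, all of whom fall within the population described in Section 1.4.

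| Patient | Section 5.1 | Section 5.2 read as any past lower GI endoscopy | Section 5.2 read as the index procedure |
|---|---|---|---|
| Upper GI index procedure, no past lower GI endoscopy | meets | can enter | can enter |
| Upper GI index procedure, past lower GI endoscopy | meets | excluded | can enter |
| Lower GI index procedure only | fails | cannot enter | cannot enter |

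The third row is the same on both readings: 0 of the 30 patients can enter for a lower GI index procedure. The second row depends on the reading.

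**3. Which reading the text favours.** Section 5.2 sets no time limit, so the literal reading is any past lower GI endoscopy. Because Section 5.1 already shuts out patients invited for a lower GI procedure only, the literal reading is also the one that gives Section 5.2 a clear effect of its own. On the index reading the clause adds little, beyond settling visits where both procedures are done. The text does not decide the matter.

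**4. Effect on variation.** If the literal reading applies, patients with lower GI experience are left out systematically, although Section 4 seeks maximal variation and Section 2.1 is about patients' experiences. The number lost would be the share of upper GI patients with a past lower GI endoscopy, multiplied by the number screened. The protocol gives neither figure, so no size can be computed.

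**5. Is the limit explained or carried through?** Sections 1.2 to 1.4, 2.1, 2.2, 3.2, 4 and 6.2 give no reason for restricting patients to upper GI, and none says that the patient conclusions will be confined to it.

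**The case against.** Restricting 30 interviews to one type of procedure is a legitimate design choice, and the protocol need not admit lower GI patients. The exclusion may well have been meant for the index procedure. Patients are approached before or after their endoscopy (Section 1.4), and Section 6.3 provides telephone consent for those who have already had it, so the past tense in Section 5.2 could simply mirror the invitation wording in Section 5.1. The harm to the staff–patient comparison is also limited. The two data sets are analysed separately first, staff who handle colonoscopes and other GI scopes also handle upper GI scopes, and the key questions in Section 3.1 (risk from reuse or disposal, environmental impact) are not tied to a scope type. Finally, Section 2.2 speaks of contributing to an overall aim that other work packages also serve.

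Most of this stands, and it limits the point to a contradiction and an ambiguity. It does not remove them. A deliberate upper GI focus would have to appear in the population, the objective and the reach of the conclusions, and it does not. An exclusion that can be read in two ways still has to be settled before sites can apply it uniformly.

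**Conclusion.** The contradiction is established from the text: patient eligibility is narrower than the stated population, objective and use of the findings, with no reason given and no matching limit on the conclusions. No patient can enter for a lower GI index procedure, whichever way Section 5.2 is read. The further loss of upper GI patients with past lower GI endoscopy holds only on the literal reading, and its size and direction are unknown.

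A reader might infer more, but the documents do not support it:

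- *No participant could speak about lower GI endoscopy.* This is true only on the literal reading. On the index reading, an upper GI patient with a past colonoscopy is eligible and can describe it.
- *The sample is skewed towards younger or endoscopy-naive patients.* Nothing in the protocol links past lower GI endoscopy to age, and age is a variation parameter. Repeat upper GI endoscopy is not excluded.
- *Screening becomes a burden.* This would need the share of upper GI patients with a past lower GI endoscopy, which is not given.
- *Complex procedures are barred.* Section 4 says "Some sites will be large tertiary centres which do complex endoscopic procedures", while Section 5.1 mentions diagnostic and less complex therapeutic work. It does so as examples of what is included, which leaves complex upper GI procedures eligible.
- *The protocol promises patient conclusions for all GI endoscopy.* It does not say so. The fault is that it sets no limit.

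**What to change.** (a) Reword Section 5.2 to refer to the index procedure, for example *index procedure is a lower GI endoscopy only*. State that past lower GI endoscopy is allowed, and record it with the procedure and endoscope type already collected under Section 7.1. The word *only* would admit a patient having both procedures at one visit, so the sponsor should confirm that this is intended.

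(b) Restate the patient population, objective and conclusions as upper GI endoscopy in the Study Summary and Sections 1.4, 2.1, 2.2 and 6.2. Add to Section 3.2 that any staff–patient comparison is interpreted with that limit.

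The cost is a narrower patient claim and one extra recorded item. The sample size does not change. Section 10.1 gives eligibility changes as an example of a substantial amendment, so the sponsor will need to decide whether (a) is a change or a clarification.

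If conclusions on all GI endoscopy are wanted instead, the upper GI requirement in Section 5.1 and the exclusion in Section 5.2 must both change, as a substantial amendment. Deleting Section 5.2 alone would not admit lower GI patients, because Section 5.1 would still keep them out.
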